6.5. Safety Analyses

Unless otherwise specified, all safety analyses will be performed based on All Treated Population. Tables and figures will be generated by cohort (Cohort 1, 2, 3, 4) and generated for Cohort 4 separately by different dosage levels of TAS-120.

6.5.1. Extent of Exposure

6.5.1.1. Administration of Study Drug

The following parameters will be summarized:

- Duration of treatment
- Number of cycles treated
- Number of doses received
- Cumulative dose
- Relative dose intensity

Duration of treatment (days) will be calculated as: 1) calculate Date of last dose – Date of first dose + 1 for each treated cycle; 2) sum up across all treated cycles.

Cumulative dose is sum of the doses administered to a subject during the treatment period.

Relative dose intensity will be calculated as cumulative dose (dose received) divided by dose planned (taking the dosing cycle into consideration)

A by-patient listing of dosing of study drug and listing of batch number will be also provided.

6.5.1.2. Modification of Study Drug

The number and percentage of patients with at least one dose interruption along with reason for the interruptions will be summarized.

The number and percentage of subjects with at least one dose reduction and reason for the dose reduction will be summarized.

The number and percentage of subjects with at least one dose discontinuation and reason for the dose discontinuation will be summarized.

By-patient listings of dose interruption, dose reduction and dose discontinuation will be also provided.

6.5.2. Adverse Events

6.5.2.1. Deaths

On-treatment deaths and reasons for death will be summarized.

A by-patient listing of all deaths occurring during screening, on treatment, 30-day safety follow-up, or survival follow-up periods will be provided.

6.5.2.2. Adverse Events

An adverse event (AE) is any untoward medical condition that occurs in patients while participating in this clinical study. Adverse events will be coded according to the Medical Dictionary for Regulatory Activities (the most up-to-date version at the time of analysis) terminology and the severity of the toxicities will be graded according to NCI CTCAE (Version 5.0 or most up-to-date version at the time of analysis), where applicable.

A treatment-emergent AE (TEAE) is defined as an AE that is starting or worsening at the time of or after the first dose of study drug administration and within 30 days after the last dose of study drug, and do not necessarily have a causal relationship to the use of the study drug. All AEs captured in the database will be listed; however, only TEAEs will be summarized.

The following AE summary tables will be generated:

- 1) Summary of AEs with the number and percentage of patients reporting AEs, serious AEs, grade ≥ 3 AEs, AEs leading to study drug discontinuation, interruption and dose reduction, and AEs with outcome of deaths.
- 2) Summary of treatment-related AEs with the number and percentage of patients reporting AEs, serious AEs, grade ≥ 3 AEs, AEs leading to study drug discontinuation, interruption and dose reduction, and AEs with outcome of deaths.
- 3) Summary of AEs by worst CTC Grade (grade 1, 2, 3, 4, 5, any grade, Grade ≥ 3) presented by System Organ Class (SOC) and Preferred Term (PT).
- 4) Summary of treatment-related AEs by worst CTC grade (Grade 1, 2, 3, 4, 5, any grade, Grade ≥ 3) presented by SOC and PT.
- 5) Grade \geq 3 AEs by worst CTC Grade (grade 3, 4, 5, 3-5) presented by SOC and PT.
- 6) Grade ≥ 3 treatment-related AEs by worst CTC Grade (grade 3, 4, 5, 3-5) presented by SOC and PT.
- 7) Summary of AEs leading to death by SOC and PT.
- 8) Summary of the most common AEs (≥10% incidence) and median time to first AE by SOC and PT.

6.5.2.3. Adverse Events Leading to Discontinuation of Study Drug

AEs leading to discontinuation will be summarized:

- Summary of AEs leading to discontinuation of study drug by worst CTC Grade (grade 1, 2, 3, 4, 5, any grade, Grade ≥ 3) presented by SOC and PT
- Summary of treatment-related AEs leading to discontinuation of study drug by worst CTC grade (Grade 1, 2, 3, 4, 5, any grade, Grade ≥ 3) presented by SOC and PT

A by-patient listing of AEs leading to discontinuation of study drug will also be provided.

6.5.2.4. Adverse Events Leading to Dose Modification of Study Drug

AEs leading to dose modification (including dose interruption and reduction) of study drug will be summarized:

- Summary of AEs leading to dose modification of study drug by worst CTC Grade (grade 1, 2, 3, 4, 5, any grade, Grade ≥ 3) presented by SOC and PT
- Summary of treatment-related AEs leading to dose modification of study drug by worst CTC grade (Grade 1, 2, 3, 4, 5, any grade, Grade ≥ 3) presented by SOC and PT

A by-patient listing of AEs leading to dose modification of study drug will also be provided.

6.5.2.5. Serious Adverse Events

Serious adverse event (SAE) will be summarized:

- Summary of SAEs by worst CTC Grade (grade 1, 2, 3, 4, 5, any grade, Grade ≥ 3) presented by SOC and PT
- Summary of treatment-related SAEs by worst CTC Grade (grade 1, 2, 3, 4, 5, any grade, Grade ≥ 3) presented by SOC and PT

A by-patient listing of SAEs will also be provided.

6.5.2.6. Adverse Events of Special Interest

Incidence

Adverse event of special interest (AESI) will be summarized:

- Summary of AESI with the number and percentage of patients reporting AESI, serious AESI, grade ≥ 3 AESI, AESI leading to study drug discontinuation, interruption and dose reduction, and AESI with outcome of deaths.
- Summary of AESI by worst CTC grade (grade 1, 2, 3, 4, 5, any grade, Grade ≥ 3) presented by category or subcategory / PT

A by-patient listing of AESI will also be provided.

Time to Onset

Time-to-onset of selected AESI (e.g. hyperphosphatemia) will be graphically displayed using the Kaplan-Meier technique.

- Time-to-onset of any grade AESI
- Time-to-onset of Grade >3 AESI

The derivation of time-to-onset of AESI is detailed in Section 8.4.

Time to Resolution

Time-to-resolution of selected AESI (e.g. hyperphosphatemia) will be summarized.

• Time-to-resolution of Grade ≥3 AESI

The following summary statistics will be reported: percentage of subjects who experienced the specific events, percentage of subjects with resolution of the AESI (clustered), median, 1st quartile and 2nd quartile of time-to-resolution along with 95% CI (derived from Kaplan-Meier estimation) and ranges.

Time-to-resolution of Grade ≥3 AESI (e.g. hyperphosphatemia) will be graphically displayed using the Kaplan-Meier technique.

Time-to-resolution analyses are restricted to patients who experienced the specific events. Collapsing selected AE and derivation of time-to-resolution of AESI is detailed in Section 8.5.

6.5.2.7. Dose Limiting Toxicity (Cohort 4 only)

The number and percentage of patients with dose limiting toxicity (DLT) will be presented by different dose levels of TAS-120. The patients with DLT will also be listed.

6.5.2.8. Multiple Events

The following summary tables will be provided:

- A table showing the total number and rate (exposure adjusted) of occurrences for all AEs by SOC and PT
- A table showing the total number and rate (exposure adjusted) of occurrences for AESI by category / subcategory

The exposure adjusted incidence rate per X patient time is calculated as $X \times Y \times$ (total number of unique AEs) / (total exposure time), where:

X = user-specified time factor, X = 1000 or 100

Y = 365.25 for years or Y = 30.4375 for months

For example, Incidence rate per 100 person-years of exposure (IR/100 P-Y) is calculated as 100 x 362.5 x (total number of unique AE count) / (total exposure time in days).

Unique instances of all AEs (that is, after duplicates have been eliminated and overlapping and contiguous occurrences of the same event (same PT) have been collapsed) will be summarized (0 event, 1 event, 2-3 events, \geq 4 events) by PT. Unique instances of AESI will be summarized (0 event, 1 event, 2-3 events, \geq 4 events) by category/subcategory.

Unique instances of all AEs will be listed.

The algorithm of collapsing selected AE records is detailed in Section 8.5.

6.5.3. Clinical Laboratory Evaluations

Clinical laboratory results will be summarized using SI units. Laboratory measurements will be summarized for each parameter. Descriptive statistics (n, mean, standard deviation, median, minimum and maximum) will be presented for clinical chemistry, hematology and coagulation parameters at each scheduled visit. Change from baseline will be summarized in a similar manner.

Laboratory test results will be graded by NCI CTCAE (Version 5.0 or most up-to-date version at the time of analysis). Shift tables will be presented for each laboratory parameter to display the shift from baseline grade to the worst post-baseline grade. Summary tables will be provided presenting the number and percentage of patients for each laboratory test by baseline grade and worst post-baseline grade. All post-baseline assessments (including unscheduled visits) will be used to determine the worst post-baseline grade. Time to maximum Grade 3/4 and time to resolution (return to grade <=2 or baseline grade or below) may be summarized as appropriate.

All clinical laboratory data will be presented in by-patient listings.

The laboratory tests of Hematology, Coagulation, Serum chemistry are listed in Table 9.

Table 9. Laboratory Tests

Assessment	Test Items	
Hematology and Coagulation	Red blood cell count, hemoglobin, hematocrit, platelets, white blood cell count with differential (absolute neutrophil count (ANC), lymphocytes, monocytes, eosinophils, basophils), Prothrombin time-international normalized ratio (INR), Activated partial thromboplastin time (APTT), fibrinogen	
Chemistry (Serum or plasma)	AST, ALT, alkaline phosphatase (ALP), total bilirubin, direct bilirubin, albumin, lactate dehydrogenase, inorganic phosphorus, triglyceride, total cholesterol, creatinine, urea or blood urea nitrogen, sodium, potassium, chloride, calcium (corrected value), magnesium, blood glucose, creatinine clearance (if there is a measured value, use the measured value) or estimated glomerular filtration rate (eGFR)	

For a calculated creatinine clearance (Ccr) value, use the Cockcroft-Gault formula:

Male Ccr (mL/min) = weight (kg)×(140-age(years))/[72×serum creatinine (mg/dL)]

Female Ccr (mL/min) = male Ccr \times 0.85

6.5.3.1 Ophthalmological Examination

Ophthalmological examination is performed at screening (within 28 days prior to TAS-120 administration on Day 1 of Cycle 1), 4-6 weeks after starting treatment with TAS-120, end of treatment visit and 30 days after last dose of study drug. Ophthalmological examination encompasses external ocular examination, slit lamp biomicroscopy and dilated ophthalmoscopy. The results of each test will be summarized by scheduled time point. All ophthalmological examination results will be listed in by-patient listing.

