Collectively, safety data from clinical trials suggest that TAS-120 is tolerable to patients with advanced cancers. The most frequently reported treatment-related adverse event (AE) overall has been hyperphosphatemia, mostly of National Cancer Institute – Common Terminology Criteria for Adverse Events (NCI-CTCAE) Grades 1-2 and without clinical complications. Other frequently reported treatment-related AEs included the gastrointestinal system disorders of diarrhea, dry mouth, nausea, and stomatitis. Dry skin and increased liver enzymes were also reported, most of which were mild to moderate in severity.

Safety concerns that have been identified from preclinical studies of TAS-120 include an increase of inorganic phosphorus in plasma, ectopic mineralization in various organs and tissues, lesions in bone/cartilage, and corneal lesions. An embryo-fetal developmental toxicity study conducted in rats showed that TAS-120 inhibited normal development of the rat embryo-fetus and resulted in embryo-fetal lethality. Effective contraception is mandated for any patients receiving TAS-120 who are of child bearing potential and their partners.

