6.1.3. Ophthalmological Examination

The cornea and conjunctiva are readily visible tissues, and therefore, abnormalities of the cornea and conjunctiva can usually be recognized via external ocular examination and routine slit lamp biomicroscopy. The retina is visible through fundoscopy after dilation of the pupil. Ophthalmologic examination will be performed at screening and 4-6 weeks after first dose; additional on-study evaluation as needed due to local requirements, physician judgment, and/or symptoms or signs of mineral deposits.

Each evaluation will encompass:

- 1 External ocular examination
- 2. Routine slit lamp biomicroscopy of anterior ocular structures, including the anterior and posterior chambers (Fluorescein or rose Bengal or other dyes used to evaluate the ocular surface can be used according to institutional guidelines and local clinical practice)
- 3. Dilation of the pupil with direct/indirect fundoscopy per institutional guidelines and local clinical practice

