6. STATISTICAL ANALYSIS

6.1. General Methods

All recorded data will be presented in listings.

The categorical data will be summarized using frequency counts and percentages of patients. The continuous data will be summarized using number of non-missing observation (n), mean, standard deviation (SD), median, minimum and maximum unless otherwise specified.

Summary tables will be presented by cohort. Data listings will be presented with patient ID and cohort.

For concomitant medications/therapy and adverse events, the cycle number is determined based on their start/onset dates. For other collected data, the cycle number is determined based on their visit dates. These data include Lab test, Physical exam, Vital signs, Height and Weight, Ophthalmological exam, ECOG, ECG, Pregnancy test, Circulating tumor DNA (ctDNA), tumor biopsies, Scheduled tumor assessment.

When there are multiple laboratory records for a scheduled visit, the one closest to the target date will be used for analysis. If there are two or more records with the same time period to the target date, the record with the latest database entry date will be used for analysis.

Time to event distribution (e.g. progression free survival, overall survival, duration of response, time to onset of AESI in a specific category, time to resolution of AESI in a specific category) will be estimated using Kaplan Meier techniques. The number of events and censorings will be reported. When appropriate, the median along with the corresponding log-log transformed 95% CI will be estimated. Rates at fixed time points will be derived from the Kaplan Meier estimate and corresponding confidence interval will be derived based on Greenwood formula for variance derivation and on log-log transformation applied on the survivor function S(t). Confidence intervals for binomial proportions, ORR, CRB, CR rate and 6-month PFS rate, will be derived using the Clopper-Pearson method.

All the analyses of efficacy, safety, and pharmacodynamics data for this study will be performed using SAS® statistical software package, Version 9.3 or a higher version.

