6.5.5. Electrocardiograms

ECG measurements include HR, RR interval, QT interval and its Fridericia's correction and Bazett's correction, and clinically abnormal findings. QTcF (Fridericia's correction) is calculated as QT/RR^{0.33}. QTcB (Bazett's correction) is calculated as QT/RR^{0.5}. Each ECG parameter will be summarized with descriptive statistics by scheduled time point. Change from baseline will be summarized in a similar manner.

Shift tables will present changes from baseline in ECG interpretation (categorized as normal, abnormal not clinically significant, abnormal clinically significant) to the worst post-baseline result.

In addition, the number and percentage of patients with at least one post-baseline abnormal ECG result in QTcF during on-treatment period will be summarized. Clinically abnormal ECG results in QTcF will be categorized as follows:

Absolute QTcF interval prolongation:

- QTc interval <= 470 ms
- QTc interval >470 480 ms (with baseline QTc interval ≤ 470)
- QTc interval > 480 500 ms (with baseline QTc interval ≤ 480)
- QTc interval > 500 ms (with baseline QTc interval ≤ 500)

Change from baseline in QTcF interval:

- OTC interval increases from baseline <= 30 ms
- OTC interval increases from baseline 30 60 ms
- QTC interval increases from baseline > 60 ms

All ECG data will be presented in by-patient listings.

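### The SAP has no any-time or worst-post-baseline summary of eye examinations, so a transient finding at an as-needed examination that is not reported as an AE reaches only the listing

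*SAP*

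**What the plan says.** SAP 6.5.3.1 sets the eye examinations at screening and then "4-6 weeks after starting treatment with TAS-120, end of treatment visit and 30 days after last dose of study drug". It plans one tabulation: "The results of each test will be summarized by scheduled time point". It also provides a listing: "All ophthalmological examination results will be listed in by-patient listing". It mentions neither as-needed examinations nor a shift, worst-result or any-time summary.

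Protocol 6.1.3 fixes examinations at screening and 4-6 weeks and adds "additional on-study evaluation as needed due to local requirements, physician judgment, and/or symptoms or signs of mineral deposits". The Schedules of Events in both documents carry the same provision and also mark end of treatment and the 30-day visit.

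Other SAP sections go further:

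- **Laboratory data (6.5.3):** "All post-baseline assessments (including unscheduled visits) will be used to determine the worst post-baseline grade".
- **ECG (6.5.5):** "Shift tables will present changes from baseline in ECG interpretation", taken to the worst post-baseline result.
- **ECOG status (6.5.7):** a shift to the worst post-baseline grade.

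Protocol 1.2.2 names the preclinical safety concerns, among them "ectopic mineralization in various organs and tissues, lesions in bone/cartilage, and corneal lesions".

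**The concern.** After the 4-6 week examination, nothing is fixed until treatment ends. In between, a patient has an eye examination only if something prompts it. An examination prompted by symptoms or signs is more likely to show a finding than a routine one, yet the planned summary is built on the routine ones.

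At stake is how clearly the study report describes ocular safety for a drug with corneal lesions and ectopic mineralization among its preclinical signals. A reader will want to know how many patients had an eye finding on treatment that was absent, or milder, at baseline. The planned table does not answer that.

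**Working it through.** The documents state no figure on this point, so the check compares the texts.

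**1. Which examinations have a place in the table.** SAP 6.5.3.1 names one baseline and three post-baseline time points: 4-6 weeks, end of treatment, and 30 days after the last dose. As-needed examinations have no fixed time.

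**2. Whether another rule places them.** SAP 6.1 covers eye examinations in its general rule: "For other collected data, the cycle number is determined based on their visit dates". That gives an extra examination a cycle number. It does not assign the examination to the 4-6 week or end-of-treatment time point, and no other section does so.

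**3. How long the uncovered interval lasts.** It runs from week 6 to end of treatment. For a patient treated for 24 weeks (an illustrative duration, assumed here), that is 24 − 6 = 18 weeks in which any eye examination is as-needed.

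**4. What happens to a finding first seen in that interval.**

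| Course of the finding | Eye table | Listing | AE tables |
|---|---|---|---|
| Still present at end of treatment | Yes | Yes | If reported as an AE |
| Cleared before end of treatment, clinical impact | No | Yes | Yes, if Protocol 8.4.1 is followed |
| Cleared before end of treatment, not reported as an AE | No | Yes | No |

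The third row is the gap. Protocol 8.4.1 makes a new instrumental abnormality an AE when it has clinical impact, such as a dose reduction, a treatment delay or an intervention. A slit-lamp finding judged to have none of these may go unreported as an AE, although the general definition in Protocol 8.1.1 is wide enough to include abnormal diagnostic results.

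**5. What the by-time-point table can show.** Suppose *a*, *b* and *c* patients of *N* have a finding at the three post-baseline time points. The number with a finding at any of them lies between max(*a*, *b*, *c*) and min(*N*, *a* + *b* + *c*), and the table does not say where. It also cannot separate new from pre-existing findings. Exclusion criterion 10c removes only retinal or corneal disorders that the investigator considers clinically significant, so patients with lesser baseline abnormalities can enter. This limit applies even if no as-needed examination is ever done.

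**6. Comparison with the other safety data.** Laboratory, ECG and ECOG results each have a worst-post-baseline summary. Only the laboratory text says explicitly that unscheduled visits count.

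**The case against.** The strongest reply is that clinically relevant eye findings already have a route into the tables. One that leads to a dose hold or reduction is an AE under Protocol 8.4.1 and enters the treatment-emergent AE tables (SAP 6.5.2.2) and the dose-modification tables (SAP 6.5.2.4). Neither depends on scheduled visits, and a symptomatic finding also meets the AE definition. This stands, and it confines the gap to findings not reported as AEs. The tables of AEs of special interest are not a sure further route, because the examples in SAP 6.5.2.6 and 8.3 include no eye category.

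Other points that stand:

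- Every result is listed, and no cohort is planned beyond about 55 response-evaluable patients, so a reader could count by hand. A listing still gives no rate, and the SAP lists laboratory and ECG data too while tabulating the worst result.
- An as-needed examination inside the 4-6 week window, or one that serves as the end-of-treatment examination, could be counted there. The Schedule of Events marks conditional eye examinations under later cycles, and the SAP does not say whether those could have their own row.
- Vital signs (SAP 6.5.4) are also summarized only by scheduled time point, and physical examination (6.5.6) is listed only. The SAP is therefore not uniform in using worst-value summaries.
- Protocol 10.5.3 promises no ophthalmology table, so no protocol commitment is broken.
- Eye results have no ordered scale in the documents, so a shift to the worst result first needs one.

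**Conclusion.** The point holds as a modest gap in safety reporting. SAP 6.5.3.1 has no any-time or worst-post-baseline eye summary. A result from an as-needed examination between week 6 and end of treatment that clears before treatment ends appears only in the listing unless it is reported as an AE. The planned table also cannot give the number of patients with a new finding relative to baseline. This rests on reading SAP 6.5.3.1 as limited to the time points it names.

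A reader might infer more in three ways, none supported by the documents:

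- **That triggered findings never reach a table.** Persistent findings are tabulated at end of treatment, and those with clinical impact should be in the AE tables.
- **That the treatment-emergent rate is biased downward.** The SAP derives treatment-emergent rates from AEs (6.5.2.2 and 8.2). The eye table shows results at each time point and is not a cumulative rate.
- **That the shortfall can be quantified.** If 10% of patients had a finding and 0%, 25%, 50% or 75% of those were seen only at triggered visits, then 10% × (1 − share) gives 10%, 7.5%, 5% or 2.5%. Both inputs are assumed, the range includes no effect, and the formula treats a by-time-point table as an ever-affected rate.

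The size therefore cannot be derived from the documents. Primary endpoints, sample size and error rates are untouched. The change is worth making because corneal lesions are a named preclinical concern and it needs no new data.

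**What to change.** Keep the by-time-point table and add the following to SAP 6.5.3.1:

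1. For each test (external, slit lamp, fundoscopy), a shift table from baseline to the worst post-baseline result, with an explicit statement that all post-baseline examinations count, including unscheduled ones.
2. An ordered categorization to define "worst". The three levels that SAP 6.5.5 uses for ECG interpretation would serve: normal; abnormal without clinical significance; abnormal with clinical significance.
3. The number and percentage of patients with any new or worsened finding relative to baseline.

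The cost is one more table and a categorization to define and apply to results already collected. The reported eye-finding rate may be higher. No examination is added and no clinical procedure changes.
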